#### **4.4. Lost to Follow-up**

Patients are considered as being lost to follow-up if they fail to return for scheduled evaluations and cannot be contacted by the site. The following actions must be taken if the patient fails to return to the clinic for a required trial evaluation:

- The trial site must attempt to contact the patient and reschedule the missed evaluation as soon as possible and counsel the patient on the importance of maintaining the assigned evaluation schedule.
- Before a patient is deemed lost to follow-up, the Investigator or designee must make every effort to regain contact with them or next of kin by, for example, repeat telephone calls, certified letter to the patient's last known mailing address, or local equivalent methods. At least 3 unique documented contact attempts to follow-up should be made and documented in the patient's records.

## 5. INVESTIGATIONAL PLAN

### 5.1. Overall Trial Design

This is a Phase 3, double-blind, randomized 2:1 (active to placebo), placebo-controlled, multi-center trial designed to assess the effect of setmelanotide on weight loss and hunger in patients with a diagnosis of acquired HO. Approximately 120 patients (at least 12 from sites in Japan) aged 4 years and older are planned to be enrolled at up to 35 clinical sites in North America, Europe, and Japan).

The trial design is depicted in [Figure 1](#).

CCI [REDACTED]

[REDACTED]

[REDACTED]

[REDACTED]

[REDACTED]

#### 5.1.1. Screening Period

The Screening Period will last up to 8 weeks (from Day -56 to -1 with a minimum of 3 weeks to allow for the completion of all necessary tests and evaluations, including the collection of CCI [REDACTED] baseline data for 2-3 weeks prior to randomization). Upon providing informed consent, patients will complete all screening procedures as listed in the SoAs to determine if they meet the study criteria.

At the Screening Visit, all patients will be given and instructed on how to use:

- a wearable actigraphy device to measure activity and sleep;
- a hand-held device for recording daily diary information throughout the study; and
- an ambulatory blood pressure monitor (ABPM) (patients  $\geq 4$  years of age, as applicable. See Section 6.8.2 for conduct in patients  $< 12$  and regional applicability of assessment). CCI [REDACTED]

Patients who are determined not to be eligible will be asked to return their devices to the clinic. See Section 6 for instructions on how these data should be collected during the Screening Period.

#### 5.1.1.1. Rescreening

Screening assessments (labs) may be repeated once to establish trial eligibility within the screening period. If repeat values of the screening assessments meet eligibility criteria and are completed within the screening window, then the patient is eligible for the trial.

If a patient screen fails due to one of the following tests, screening can be repeated for: CCI later and T4 up to 60 days later. If a patient is rescreened for out-of-range lab results those results will be re-tested and the updated values will be captured on a rescreen form in electronic data capture (EDC).

#### 5.1.2. Treatment Period

To enter the Treatment Period on Day 1 and prior to randomization, the trial center must confirm that patients have completed the Screening assessments, including the e-diary at least 4 of the 7 days prior to the baseline visit. If the e-diary is not appropriately completed before the baseline visit, patients may be asked to complete the e-diary collection and re-schedule randomization and the baseline visit if the remaining visit window allows. Throughout the trial, patients (or caregivers) will need to complete the e-diary entries.

The Treatment Period will last up to 60 weeks. Trial drug administration details are provided in Section 5.5.3. During the Treatment Period, patients will attend the in-clinic visits and may attend at-home tele-health visits at Weeks 8, 16, 20, 28, 36, 44, 52 at the discretion of the investigator. Patients and caregivers will complete the assessments listed in the SoA (Table 1). Detailed assessment information is provided in Section 6.

CCI

#### 5.1.3. End of Treatment

The End of Treatment (EOT) visit will occur as an in-person clinic visit after 52 weeks on a therapeutic regimen, which is the final planned week of dosing with trial treatment. At the EOT, patients who complete 52 weeks on a therapeutic regimen and complete assessments through the EOT visit may be eligible to enter an open-label LTE trial or attend Bridging visits with open-label setmelanotide if the LTE is not yet available. Patients must meet the LTE eligibility criteria and should discuss eligibility with the Investigator.

CCI

All patients who discontinue treatment prematurely should attend an ETT Visit as soon as possible after the last dose of trial treatment. Patients who discontinue treatment but remain enrolled in the trial should continue to complete assessments (as Retained Dropouts). These patients will be required to complete the SFV as applicable following the ETT (Section 5.1.4). Patients who discontinue treatment prematurely are not eligible to enroll in the optional LTE trial. Exceptions may be made in consultation with the Sponsor.

Patients who discontinue prematurely and withdraw from the trial will not be required to complete the SFV following the ETT.

If the ETT Visit occurs 4 weeks or later following the last dose of trial treatment, then the ETT Visit will replace the SFV if no AEs are being monitored.

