**CCI**  

#### **4.3. Treatment Discontinuation and Withdrawal from Trial**

Given this rare patient population, every effort should be made to encourage and keep patients enrolled in the trial until completion, unless there are any safety concerns necessitating withdrawal of the trial treatment or the patient from the trial. If patients must discontinue

treatment, they should be encouraged to continue to participate in all regular trial visits and assessments (other than dosing and pharmacokinetic [PK] assessments), if possible, as a Retained Dropout.

The Sponsor will provide assistance for patient and caregiver travel and will provide other necessary logistical support to ease the burden on the patient in order to facilitate compliance and completion of trial participation.

Discontinuation of trial treatment or skipped visits/doses may be allowed without withdrawal from the trial upon consultation with the Sponsor and CRO Medical Monitor.

Patients who either discontinue treatment or withdraw from the trial before completing the trial are to attend an Early Termination of Treatment (ETT) Visit as soon as possible after the last dose of trial treatment. Patients who prematurely discontinue treatment may also be required to complete the Safety Follow-up Visit (SFV), if applicable (Section 5.1.4).

If the ETT Visit occurs 4 weeks or later following the last dose of trial treatment, then the ETT Visit will replace the SFV if no ongoing AEs are being monitored. Patients who prematurely discontinue study drug treatment will continue to complete all scheduled study visits for assessments following completion of the ETT.

Patients who complete the trial will have the opportunity to participate in the LTE with open-label setmelanotide (or Bridging visits if the LTE is not yet available). Patients must meet the LTE eligibility criteria and should discuss eligibility with the Investigator.

Patients who discontinue trial treatment but remain in the trial should be encouraged to attend all planned visits until the final Visit. See Section 5.1.3. Patients who discontinue treatment will be counted as non-responders, irrespective of treatment assignment. Patients who discontinue treatment prematurely are not eligible to enroll in the optional LTE. Exceptions may be made in consultation with the Sponsor.

Patients who withdraw from the trial will attend an ETT visit only.

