If the patient withdraws consent for disclosure of future information, the Sponsor may retain and continue to use any data collected before such a withdrawal of consent.

If a patient withdraws from the trial, he/she may request destruction of any samples taken and not tested, and the Investigator must document this in the site trial records and inform the Sponsor.

Patients will be informed that they have the right to withdraw from the trial at any time for any reason, without prejudice to their medical care. The Investigator also has the right to withdraw patients from the trial for reasons such as:

- AEs, which in the opinion of the Investigator justifies treatment or trial withdrawal. For specific predefined events, additional monitoring and guidance for the Investigator is provided in [Appendix 5](#).
- Non-adherence to trial medication regimen or protocol requirements.
- Non-compliance with instructions or failure to return for follow-up.

All patients who withdraw prior to completing the treatment period should be strongly encouraged to complete the ETT visit as outlined in the SoAs (Table 1, CCI ), even if they are no longer receiving trial medication.

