#### **5.5.2.2. Replacement of Patients**

Patients who withdraw or are withdrawn from the trial after randomization will not be replaced. Randomization will not be revised once a patient is randomized.

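### The waiver of the safety follow-up visit for patients who withdraw is not tied to withdrawal of consent, and one reading ends scheduled collection of new AEs up to 14 days before the TEAE window closes

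*Protocol*

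**What the plan says.** The waiver:

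- Protocol Section 5.1.3, the synopsis (End of Treatment) and SAP Section 1.3.1 carry the same sentence: "Patients who discontinue prematurely and withdraw from the trial will not be required to complete the SFV following the ETT."
- Protocol Section 4.3 adds: "Patients who withdraw from the trial will attend an ETT visit only."

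Who can be withdrawn:

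- Section 4.3 says that "The Investigator also has the right to withdraw patients from the trial for reasons such as" those it then lists. The first is "AEs, which in the opinion of the Investigator justifies treatment or trial withdrawal"; the others are non-adherence and non-compliance.
- Its closing sentence gives a single instruction on the ETT: "All patients who withdraw prior to completing the treatment period should be strongly encouraged to complete the ETT visit."
- On timing, Section 5.1.3 says: "All patients who discontinue treatment prematurely should attend an ETT Visit as soon as possible after the last dose of trial treatment."

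Who keeps the SFV:

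- Of patients who stop treatment but stay enrolled (Retained Dropouts), Section 5.1.3 says: "These patients will be required to complete the SFV as applicable following the ETT."
- Schedule of Assessments (SoA) footnote 2 and schema note b tie the SFV to premature discontinuation. Section 5.1.4 sets it at 14 ± 4 days after the last dose and exempts only certain completers. None of the three exempts patients who withdraw.

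When AE collection ends:

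- The SoA collects AEs up to completion of trial participation. Under Section 5.1.6, a patient who stops early without withdrawing consent completes participation at the latest of the EOT, the ETT and, where it is required, the SFV.
- Section 6.10.1 runs AE collection to the SFV. It also says Investigators need not actively look for AEs in former patients.
- SAP Section 4.5.2 counts an AE as treatment-emergent if it starts after dosing and within 14 days of the last dose.

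**The concern.** Withdrawal from the trial is a wider category than withdrawal of consent. A patient whom the Investigator removes because of an AE may be willing to be contacted, yet the waiver can be read as covering that patient. If so, nothing is scheduled after an ETT that is itself meant to happen as early as possible.

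New events in the days after the last dose are of most interest in exactly such a patient. The SFV also carries safety laboratory tests and the depression and suicidality questionnaires, and Section 6.8.10 requires scores over set thresholds to be reported as AEs. Elsewhere, Sections 4.3 and 5.1.3 let an ETT stand in for the SFV only if it falls at least 4 weeks after the last dose and no AEs are being monitored. The waiver carries neither condition.

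Sites could also act differently while each follows the protocol. A site working from Sections 4.3 and 5.1.3 may schedule nothing after the ETT. A site working from Section 5.1.4 or SoA footnote 2 may book the SFV. What is at stake is the completeness of the post-dose part of the TEAE counts for a small group.

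**Working it through.** **Which patients the waiver covers.** Section 5.1.3 divides early discontinuers into those who remain enrolled (SFV required) and those who withdraw from the trial (SFV waived). A patient removed by the Investigator is no longer enrolled, so may be placed in the second group. No sentence in Sections 4.3, 5.1.3, the synopsis or SAP 1.3.1 adds a condition about consent. Three places lean the other way:

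- Section 5.1.6 pairs the ETT with withdrawal of consent as the end of participation.
- Section 5.5.2.2 separates the two kinds of withdrawal: "Patients who withdraw or are withdrawn from the trial after randomization will not be replaced."
- Section 7.4 stops efficacy measurement only on explicit withdrawal of consent.

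The text therefore supports both readings.

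**What follows on the broad reading.** For a withdrawn patient who still consents:

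1. The SFV is waived (5.1.3), so it is not required in the sense of 5.1.6.
2. There is no EOT visit, so participation ends at the ETT (5.1.6).
3. Scheduled AE collection ends with participation (SoA), and there is no duty to look for AEs afterwards (6.10.1).
4. The TEAE window still runs to day 14 after the last dose (SAP 4.5.2).

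**Size of the gap.** Inputs: the window ends on day 14 (SAP 4.5.2); the ETT falls on day T, as soon as possible after the last dose (5.1.3). The documents fix no value for T, so a range is shown.

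Uncovered days = max(0, 14 − T)

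| ETT on day T | Uncovered days |
|---|---|
| 0 | 14 |
| 3 | 11 |
| 7 | 7 |
| 10 | 4 |
| 14 or later | 0 |

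**With the existing SFV restored.** The SFV may fall on days 14 − 4 = 10 to 14 + 4 = 18. For a last AE check on day C, uncovered days = max(0, 14 − C): 4 for C = 10, 3 for C = 11, 2 for C = 12, 1 for C = 13, and 0 for C = 14 to 18. The maximum falls from 14 days to 4. Those 4 days are what the protocol's own window already allows for any patient who has an SFV.

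**How many patients.** Section 7.1 assumes 20% dropout but does not split it into retained, consent-withdrawn and Investigator-withdrawn patients. The number affected cannot be derived, and no estimate is made.

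**Effect on the tables.** SAP 4.5.2 counts each patient once per incidence rate. A missed event changes a rate only if that patient had no other qualifying event in the same category.

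**The case against.** The strongest case is that the waiver was meant for consent withdrawal only. Section 5.1.6 gives early discontinuers two categories, consent kept and consent withdrawn, and attaches the ETT to the second, which fits the ETT-only rule in Section 4.3. Section 7.4 shows whom the protocol expects to stop measuring. Section 4.3 says patients who stop treatment continue all scheduled visits and urges sites to keep them enrolled, so a willing patient with an AE would normally become a Retained Dropout and have the SFV. SoA footnote 2, schema note b and Section 5.1.4 also leave out the 4-week substitution rule, so their silence on the waiver is weak evidence of a contradiction. The closing sentence of Section 4.3 concerns ETT attendance and does not mention the SFV. Finally, a TEAE window defines which events count; it does not promise a visit on its last day.

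Much of this stands. A reader might infer that the broad reading is the intended or more natural one. The documents do not support that, because Sections 5.1.6, 5.5.2.2 and 7.4 give the narrow reading real weight. But no text limits the waiver to consent withdrawal, and none restores scheduled collection of new AEs for a patient withdrawn by the Investigator. Section 7.4 concerns efficacy measurement. The Retained Dropout route does not help a patient whom the Investigator has removed from the trial.

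It would also be too much to ask for a further call on days 14 to 18 after an SFV held on days 10 to 13. That would hold withdrawn patients to a stricter standard than enrolled ones.

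**Conclusion.** The point holds as an ambiguity with a bounded consequence, and correcting it is optional but cheap. At most 14 days of the TEAE window lack scheduled collection of new AEs, and fewer as the ETT moves later. This rests on four assumptions: the site adopts the broad reading; the patient is withdrawn from the trial and not only from treatment; the patient still consents to contact; and the ETT falls before day 14.

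Two stronger conclusions are tempting and are not supported:

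- A reader might infer that safety follow-up stops for anyone withdrawn because of an AE. It does not. Sections 6.10 and 6.10.3 continue follow-up of known AEs that are serious, related or the cause of discontinuation. Section 6.10.1 requires prompt notification of an SAE learned of later and judged reasonably related. SAP 4.5.2 counts events deemed related to study drug as treatment-emergent with no day limit. Retained Dropouts keep the SFV.
- A reader might infer a biased safety comparison or an effect on efficacy. Nothing in the documents shows that this kind of withdrawal differs by arm, and the efficacy analyses do not depend on the SFV waiver.

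The number of patients affected is not given and is probably small.

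**What to change.** In the synopsis, Sections 4.3 and 5.1.3, and SAP Section 1.3.1, limit the waiver to patients who withdraw consent (or assent) to further contact. All other withdrawn patients should have the existing SFV, or a safety call if they decline a visit, at 14 ± 4 days after the last dose. An ETT held in or after that window, with an AE check, counts.

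Align SoA footnote 2, schema note b, Sections 5.1.4 and 5.1.6, and the end of AE collection in Section 6.10.1. No extra call is needed after an SFV on days 10 to 13.

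The cost is wording changes in the two documents, plus one existing visit or a call for a few patients who still consent.

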#### 5.1.4. Safety Follow-up Visit

An SFV will occur as an in-person visit 14 days ( $\pm 4$  days) after the last dose of trial treatment. The SFV is not required for patients who complete the treatment period and either:

- enroll in the LTE (or bridging visits if the LTE is not yet available) or transition to another qualified Rhythm study (e.g., managed access)
- transition to a commercially available Rhythm MC4R agonist regimen

#### 5.1.5. Post-treatment Follow-up and Bridging visits

Patients who complete 52 weeks on a therapeutic regimen and remain enrolled are eligible to participate in the LTE trial. If the LTE is not yet available and the patient continues to meet inclusion/exclusion criteria, patients may initiate open-label setmelanotide via Bridging visits that occur in clinic every 12 weeks and last until either the LTE or a post-trial access program is available, commercial drug is available in the region, or the trial ends. Additional visits may be scheduled at the discretion of the Investigator. Since the patient's initial assignment to either setmelanotide or placebo will continue to be blinded to all parties, open-label dosing in Bridging visits will follow the dosing schedule outlined in Section 5.5.3.

CCI

#### 5.1.6. Completion of Trial Participation

Completion of trial participation for an individual patient is defined as 1 of the following:

- For patients who completed 52 weeks on a therapeutic regimen at the EOT and enroll in the LTE (or Bridging visits) or transition to either commercial drug or a post-trial access program: the EOT Visit

- For patients in bridging visits or who have transitioned from bridging visits to commercial drug or a post-trial access program: the last bridging visit.
- For patients who complete 52 weeks on a therapeutic regimen through the EOT Visit and do not enroll in the LTE, bridging visits, or transition to either commercial drug or a post-trial access program: the SFV
- For patients who prematurely discontinue trial treatment and complete some trial assessments but do not withdraw consent (and assent, as applicable): the latest of the EOT Visit, ETT Visit, or SFV (if required)
- For patients who withdraw consent or assent: date of withdrawal of consent or assent (ETT Visit)

CCI

The end of the trial overall is defined in Section 5.3.

## **5.2. Trial or Site Termination or Suspension**

This trial or any site may be suspended or terminated, if in the opinion of the Sponsor, there is sufficiently reasonable cause. The Sponsor will provide written notification documenting the reason for cohort/site/trial termination to the Investigator.

Circumstances that may warrant suspension or termination include, but are not limited to:

### **At the Trial level**

- Determination of unexpected, significant, or unacceptable risk to patients
- Plans to modify, suspend or discontinue the development of the trial medication

### **At the Site level**

- Failure to enroll patients at an acceptable rate

- Insufficient adherence to protocol requirements
- Insufficiently complete and/or evaluable data

If the study is prematurely terminated or suspended, the Sponsor shall promptly inform the Investigator, the Independent Ethics Committees (IECs)/Institutional Review Boards (IRBs), the regulatory authorities, and any CRO(s) used in the study about the reason for suspicion or termination, as specified by the applicable regulatory requirements. The Investigator shall promptly inform the trial patients and should ensure appropriate patient therapy and/or follow-up.

Should the trial be closed prematurely, all trial materials must be returned to the Sponsor or designee.

### **5.2.1. Trial Conduct During the COVID-19 (Coronavirus) Pandemic**

The worldwide Coronavirus Disease 2019 (COVID-19) pandemic may impact the conduct of clinical studies due to the challenges from quarantines, site closures, travel limitations, and other considerations if site personnel or trial participants become potentially exposed to or infected with COVID-19. To assure the safety of trial participants, maintain compliance with Good Clinical Practice (GCP), and minimize risks to trial integrity, if necessary, in consultation with the Sponsor, the method of assessment may be changed). In addition, site visits may be replaced with telephone, internet-based video-conferencing applications, or home visits by qualified health care professionals. Normal procedures, as detailed in this protocol, will be resumed as soon as possible thereafter. More detailed guidance on trial conduct during the COVID-19 pandemic is provided in [Appendix 7](#).

### **5.3. End of Trial**

The End of Trial is defined as the date of the last scheduled visit (or contact) of the last patient.

The last visit or contact for each patient may be an unscheduled visit, the ET visit, the EOT visit, the SFV, or a scheduled Bridging Visit.

### **5.4. Rationale for Trial Elements**

#### **5.4.1. Trial Design**

Setmelanotide is being evaluated as a potential treatment for obesity in populations with rare mechanistically induced acquired hypothalamic injury.

This Phase 3, double-blind, randomized (2:1 active to placebo), placebo-controlled, multi-center registrational trial is designed to assess the effect of setmelanotide on weight loss and hunger in patients with acquired HO  $\geq 4$  years of age. Placebo is considered the appropriate comparator since no treatment has been approved for use in patients with acquired HO.

The duration of this Phase 3 trial provides sufficient time to collect long-term controlled efficacy and safety data and demonstrate the efficacy of setmelanotide versus placebo.

CCI

CCI [REDACTED]

